12.1 Schedule of assessment

An overview of the trial conduct is provided in [Table 3](#).

Table 3: Schedule of assessments

Assessments	Screening D-2 to D0 ^g	Blinded treatment ^l					EoT	EoS D28 ±1 d	USV SFU ^p	
		D0 ^g		D1 - D5	D6	D7 - D13				
		Pre	Post							
Informed consent	•									
Demographics, incl. high risk factors ^f	•									
In-/exclusion criteria	•									
Local screening labs performed or taken from existing labs ^k	•									
Confirmation of positive SARS-CoV-2 status	• ^m									
Randomization		•								
Medical history	•									
Concomitant medications/procedures	•	•	• (daily)	•	• (daily)	•	•	•	•	
Physical examination	•			•			•			
Continuous monitoring with documentation of										
Status hospitalization/ status ICU ^c		Twice daily				•	•	•	•	
Survival status		Twice daily				•	• ⁿ			
O ₂ supplementation (incl. type of ventil.)		Twice daily				•	•	• ^p	• ^p	
Temperature		Twice daily				•		• ^p	• ^p	
Vital signs ^r		Twice daily				•		• ^p	• ^p	
Respiratory rate		Twice daily				•		• ^p	• ^p	
SpO ₂		Twice daily				•		• ^p	• ^p	
Score assessment (9-point WHO scale) ^b	•	Once daily (evening)				•	•	• ^p	• ^p	
Vasopressor dose		Once daily (evening)				•	•			
Radiol. confirmation in clinical practice of interst. lung disease ⁱ		Once daily (evening)				•				
Document confirmation of any new infections ^j		Once daily (evening)				•				
Use of RRT		Once daily (evening)				•	•	• ^p	• ^p	
Use of ECMO		Once daily (evening)				•	•	• ^p	• ^p	

Table 3: Schedule of assessments (*continued*)

Assessments	Screening D-2 to D0 ^g	Blinded treatment ^l					EoT	EoS D28 ±1 d	USV SFU^p	
		D0 ^g		D1- D5	D6	D7 - D13				
		Pre	Post							
Lab assessments										
Blood biochemistry		•			•		•	•	• ^p	
Hematology		•			•		•	•	• ^p	
Coagulation ^a		•			•		•	•		
Urinalysis		•			•		•	•	• ^p	
Disease markers ^a		•	• (daily)	•	• (daily)		•	•		
Biomarkers ^a		•			•		•	•		
IMU-838 trough levels ^a		•	• (daily)	•			• ^o	•		
SARS-CoV-2 viral load and SARS-CoV-2 status (qualitative) ^e		•	• (Days 2 & 4 only)	•	• (Days 8, 10 & 12 only)		•	•	• ^p	
Serology: SARS-CoV-2 antibodies ^h		•			•		•	•	• ^p	
Immune cell subtyping (US only) ^q		•			•		•	•		
Lab Kits used										
Kit A		•			•		•	•	• ^p	
Kit B			• (daily)		• (daily)					
Kit C		•			•		•	•		
Kit PK		•	• (daily)	•			• ^o	•		
Kit D		•	• (daily)	•	• (daily)		•	•	• ^p	
Kit E		•			•		•	•	• ^p	
Immune cell subtyping (US only) ^q		•			•		•	•		
Safety										
AE assessment	•							•	•	
ECG		•	•	• (only Day 3)	•		•	•		
IMP										
IMP administration										
Number of tablets	-	2	1 tablet each morning + evening							
Accountability								•		
SoC treatment										

^a Needs to be frozen at at least -20° C (-4° F) and sent to the central safety laboratory within 6 weeks.

^b Clinical status on a 9-category ordinal scale (as proposed by the WHO master protocol)

^c Including documentation of ICU admission and discharge times.

- d Existing local lab values obtained within 48 hours of randomization as well as locally obtained screening lab values can be used for assessment of eligibility.
- e At each time point only 1 nasopharyngeal swab and 1 sputum sample each will be taken. The viral load test will also be used as qualitative test (i.e. may be evaluated as absence or presence of virus in the quantitative SARS-CoV-2 assessments). Samples need to be frozen at at least -20° C (-4° F) and sent to the central virology laboratory within 7 days on dry ice.
- f Includes: Age≥65; cardiovascular disease (including hypertension), pre-existing pulmonary disease, diabetes, current treatment for malignancy or within the previous 3 years, immunosuppression (due to ongoing use of immunosuppressive drugs or existing disease leading to impaired immune status), body mass index.
- g Screening, randomization and first IMP administration can be performed the same day (Day 0). If screening is performed on Day 0, treatment will start with the evening dose.
- h Plasma sample for serology SARS-CoV-2 (IgG and IgA detection) should be frozen at at least -20° C (-4° F) and sent to the central safety laboratory within 6 weeks.
- i Confirmation of radiographic evidence of pulmonary infiltrates by chest X-ray or CT (only if done within the scope of routine clinical practice).
- j Confirmation of presence of any new viral or non-viral infection (this is not a protocol-required procedure, only documentation when done within the scope of routine clinical practice). Site of infection and source of culture will be recorded.
- k As performed during routine clinical practice in the center. Must include white blood cell count, platelet count, total bilirubin, alanine aminotransferase or gamma glutamyl transferase, serum creatinine, for women of childbearing potential: blood pregnancy test, and if the patient has known Gilbert syndrome: indirect [unconjugated] bilirubin.
- l For assessments, if patients will be discharged from the hospital before Day 14, see *Blinded Treatment period (Day 0 to Day 13) and Day 14 (end-of-treatment)*. For centers in Bulgaria only: Patients must be hospitalized during the entire treatment period.
- m Within 4 days of randomization.
- n If no EoS visit was performed, information about patient status should be reported on the EoS page in the case report form. If the patient is lost to follow-up, the investigator must contact the patient, the patient's family or the referring physician by phone or email to obtain survival status, or it must be possible to search in registers or publicly available information for these survival data.
- o Blood sampling must be performed in the morning around the time the morning dose was usually taken by the respective patient.
- p Safety follow up assessments must be performed regularly (at least once) by phone or email between Day 28/EoS and Day 60 and documented as an unscheduled visit in the eCRF. The patients should be asked to return for an on-site visit if the investigator deems this necessary for follow-up. The assessments not to be done if the visit is performed as a telephone or email contact in the scope of the safety follow up are marked as •^p
- q *Optional for centers in the USA only: 2 blood samples will be collected to evaluate immune cell subtypes and immune reactions for future research studies. This will be shipped directly to a US research site and not to the central laboratory. Shipment needs to be done at ambient temperature and immediately the same day after sampling.*
- r Height and weight only to be measured at D0, pre-dose.

AE = adverse event, CT = computed tomography, cont. = continued, D = day, ECG = electrocardiogram, ECMO = extracorporeal membrane oxygenation, EoS = end-of-study, EoT = end-of-treatment, ICU = intensive care unit, Ig = immunoglobulin, IMP = investigational medicinal product, incl. = including, interst. = interstitial, pre(post) = pre(post) IMP, RRT = renal-replacement therapy, Radiol. = radiological, SARS-CoV-2 = severe acute respiratory syndrome coronavirus 2, SFU = safety follow up, SoC = standard of care, SpO₂ = peripheral capillary oxyhemoglobin saturation, ventil. = ventilation, USV = unscheduled visit, WHO = World Health Organization.

12.2 Screening (Day -2 to Day 0) and Day 0

Patients for whom written informed consent (for consent procedures see Section 19.3) was obtained will undergo the assessments shown in [Table 3](#). Patients will be screened for eligibility based on the trial's inclusion and exclusion criteria. The infection with SARS-CoV-2 must have been confirmed by RT-PCR within 4 days of randomization. To assess eligibility existing local laboratory values obtained within 48 hours of randomization will be used.

Whenever possible, screening, randomization and 1st IMP administration should be performed on the same Day (Day 0). In this case the Day 0 assessments (see [Table 3](#)) will be performed, as soon

as the eligibility is confirmed. Treatment will then start with the evening dose. For dosing recommendations how to dose on initial days see Section [11.1.5](#).

12.3 Blinded treatment period (Day 0 to Day 13) and Day 14 (end-of-treatment)

Patients will undergo the assessments and procedures as detailed in [Table 3](#). Blood samples to assess IMU-838 trough levels will be taken pre-dose on Day 0 before first IMP dose is given. If patients will be discharged from hospital during the BT, they will be asked to return for a visit at Day 6 and Day 14, whatever is applicable (*not applicable for centers in Bulgaria as all patients must be hospitalized between Day 0 and Day 14*). Treatment will be stopped at Day 13 with the evening dose on that day as the last IMP administration. After the last IMP dose in the evening of Day 13, the end-of-treatment (EoT) assessments will be done on Day 14 (see [Table 3](#)). Blood sampling for IMU-838 trough values must be performed in the morning around the time the morning dose was usually taken by the respective patient.

For centers in Bulgaria: Patients must be hospitalized during the entire treatment period i.e., from Day 0 to Day 14.

For centers in countries other than Bulgaria: If applicable, the patient will be asked to return all remaining IMP and its packaging (including empty bottles) to the trial center at Day 14 for IMP accountability checks.

In case of hospital discharge before Day 14, the following assessments should be done between hospital discharge and until Day 14 (patients should return for clinic visits at Day 6, if discharged before Day 6, and Day 14):

- On the day of hospital discharge:
 - All trial-related assessments and procedures are completed as per [Table 3](#) and finalized (evening assessments should be done, even when patient is discharged during the day)
 - The date and time of hospital discharge need to be documented
- Day 6 and Day 14:
 - The full lab assessments to be performed on Days 6 or 14, respectively (as indicated in [Table 3](#))
 - Physical examination and ECG
 - Documentation of concomitant medications/procedures, AEs, temperature, vital signs, respiratory rate, type of oxygen supplementation, survival status, hospitalization status, assessment of WHO ordinal scale [\[21\]](#) (only once daily assessment required)
 - Return of IMP by patients and drug accountability (Day 14 only)

If the patient is discharged from the hospital before Day 14, the patient will receive the IMP and will take the remaining doses of IMP at home.

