Efficacy (continued)	
 • Proportion of patients 
 • with auxiliary oxygen therapy* (including all types of oxygen therapy) until Days 6, 14, and 28 • with clinical recovery defined as 
 • Axillary temperature ≤ 36.6 °C, or oral temperature ≤ 37.2 °C, or rectal or tympanic temperature ≤ 37.8 °C; and • Respiratory frequency ≤ 24 times/min without oxygen inhalation; and • Oxygen saturation $\geq 98\%$ without oxygen inhalation • With clinical improvement, defined as an improvement of at least 2 points on the WHO 9 category ordinal scale [21], or live discharge from hospital without oxygen supplementation, whichever comes first • Change in daily clinical patient status on the WHO 9-category ordinal scale [21] • Duration of INV • Duration of ECMO • Duration of RRT • Duration of auxiliary oxygen therapy (including all types of oxygen therapy) • Duration of hospitalization for survivors • Rate of ICU* admission until Days 6, 14, and 28 • Hospital-free days

Trial objectives and endpoints (continued)

Objective	Endpoint
Secondary (continued)	
Efficacy (continued)	
	
 • Time from IMP treatment initiation to death • Time to first prescription of INV • Time to first prescription of RRT • Time to first prescription of ECMO • Time to first prescription of INV, RRT, and ECMO • Time to ICU admission • Cumulative dose of vasoactive therapies and days (daily until Day 14) with vasoactive therapies (until Day 14) • Time to clinical recovery
Pharmacokinetics	
To evaluate trough plasma levels of IMU-838	
 • Morning trough plasma levels of IMU-838 on Days 0, 1 through 6, 14, and 28 • Correlation of trough levels (quartiles) to selected clinical outcomes
Safety	
To evaluate safety and tolerability of IMU-838	
 • AEs and SAEs • Vital signs • Clinical laboratory parameters (blood chemistry, hematology, and urinalysis) • Electrocardiogram (ECG) parameters • Temperature

Trial objectives and endpoints (continued)

Objective	Endpoint
Secondary (continued)	
Disease markers	
To explore blood levels of disease markers	
 • D-dimer • Lactate dehydrogenase (LDH) • C-reactive protein (CRP) • Troponin I (cTn) • Procalcitonin (PCT) • Correlation of disease markers to selected clinical outcomes

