15.3 Vital signs, physical examination, and ECG

Vital signs, routine physical examinations, and ECG will be performed as scheduled in [Table 3](#).

Vital signs

Vital signs will include height and weight (both only at Screening), body temperature (°C), pulse rates, systolic and diastolic blood pressures. Height in centimeters and weight in kilograms will be recorded without shoes.

Blood pressure (systolic and diastolic), and pulse must be measured with the patient in a seated position (if possible), after at least 5 minutes at rest.

Body temperature can be measured axillary, oral, rectal or tympanic, but should always be measured by the same method for a patient.

Changes in vital signs judged by the investigator as clinically significant will be reported as an AE.

Physical examination

Physical examinations will cover the following body systems: general appearance, skin, neck (including thyroid), throat, lungs, heart, abdomen, back, lymph nodes, extremities, vascular, neurological systems, and, if applicable, others.

Any new clinically significant finding compared to Screening must be documented as AE.

Any clinically significant finding at Screening Visit 1 must be documented in the medical history section of the eCRF.

12-lead electrocardiogram

The 12-lead ECG (I, II, III, aVR, aVL, aVF, V₁-V₆) will be recorded in supine position after at least 5 minutes at rest (if applicable) using the local standard ECG machine. The ECG will be analyzed qualitatively (normal or abnormal, if abnormal clinically significant [yes/no]). The heart rate, PQ-, QRS-, and QT-intervals, as well as the heart rate-corrected QT_c interval (according to Bazett's formula) will be determined. All procedures will be done according to local practice. Any findings from ECGs collected after the IMP administration will be captured as AEs if, in the opinion of the investigator, there was a clinically significant change from Screening.

16 Biostatistical methods

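### The Day 6 and Day 14 assessment list for patients discharged early omits SpO2, which the clinical recovery endpoints require; at Day 14 the list also conflicts with Table 3

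*Combined protocol and SAP*

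**What the plan says.** Section 7 of the protocol (and the synopsis) has a secondary endpoint for the proportion of patients "with clinical recovery defined as" three criteria joined by a logical and: temperature at or below a route-specific limit, respiratory rate of at most 24 per minute without oxygen, and SpO2 of at least 98% without oxygen. A companion endpoint is "Time to clinical recovery".

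In hospital, Table 3 (Section 12.1) has SpO2 recorded twice daily through the treatment period. For early discharge, a footnote on the blinded-treatment heading of that table redirects the reader: "For assessments, if patients will be discharged from the hospital before Day 14, see" the text describing the treatment period and Day 14. That text is in Section 12.3 and the synopsis:

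- On the day of discharge the full set applies: "All trial-related assessments and procedures are completed as per" Table 3.
- On Day 6 (only for those discharged before Day 6) and on Day 14, the list calls for the scheduled laboratory tests, physical examination, ECG, and the following: "Documentation of concomitant medications/procedures, AEs, temperature, vital signs, respiratory rate, type of oxygen supplementation, survival status, hospitalization status, assessment of WHO ordinal scale".

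Section 15.3 limits vital signs to height, weight, body temperature, "pulse rates, systolic and diastolic blood pressures".

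Centers in Bulgaria keep patients in hospital to Day 14, so the discharge list does not apply there.

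**The concern.** A composite that needs three measurements cannot be scored as met when one of them is not taken. A site that follows the discharge list would have temperature, respiratory rate and oxygen use for a returning patient, but no saturation value.

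The affected patients are those sent home before meeting all three criteria. The protocol states no saturation threshold for discharge, and entry on oxygen is allowed with SpO2 just above 92%, so leaving hospital below 98% is plausible. Discharge happens after randomization and may itself respond to treatment; duration of hospitalization is an endpoint in its own right. Missingness tied to discharge can therefore differ between arms. It can also differ by country, because patients in Bulgaria keep twice-daily SpO2 through the treatment period. Section 16.3 gives no rule for a missing recovery component.

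**Working it through.** No formula applies; the check sets the endpoint definition beside the data-collection rules.

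| Component of recovery (Section 7) | Discharge list, Days 6 and 14 (Section 12.3, synopsis) | Vital signs (Section 15.3) | Table 3 |
|---|---|---|---|
| Temperature | listed | included | twice daily in treatment period; EoT marked; no EoS entry visible |
| Respiratory rate | listed | not included | same |
| SpO2 | **not listed** | not included | same |
| Absence of oxygen | type of oxygen supplementation listed | not applicable | twice daily; EoT and EoS marked |

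1. *Could another listed item supply SpO2?* No. It is not a vital sign in Section 15.3, and Section 13.3 lists it with respiratory rate, separately from vital signs. It has its own row in Table 3 under continuous monitoring, so the instruction to do the full laboratory assessments does not reach it. The physical examination covers body systems. The WHO scale records the type of oxygen support, not a saturation value.

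2. *Day of discharge.* SpO2 is taken with the full Table 3 set. A patient who meets all three criteria by then is correctly scored.

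3. *Day 6, discharged before Day 6.* The only Table 3 entry covering this day is the in-hospital twice-daily one, which lies under the heading whose footnote redirects discharged patients to the list. The list omits SpO2, so no rule clearly requires it.

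4. *Day 14, all discharged patients.* Table 3 marks SpO2 in the EoT column, and Section 12.3 says that end-of-treatment assessments follow Table 3. The footnote, however, points to text that expressly covers Day 14, and the list there omits SpO2. The current text has no precedence rule; the revision chronology records that a clause giving the schedule precedence was removed. This is a conflict between passages, not a settled omission.

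5. *Day 28.* In Table 3 as extracted, temperature, respiratory rate and SpO2 show no EoS entry, while oxygen supplementation and the WHO score do. The recovery endpoint names no assessment day, so the documents do not say that it must be scored at Day 28.

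6. *Other visits.* Unscheduled and on-site safety follow-up visits carry SpO2, but no on-site visit of either kind is required.

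7. *Reach.* Recovery is not the primary endpoint, not a key secondary endpoint, and not among the activity endpoints in Section 16.4.2.

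**The case against.** The strongest reply is that Table 3 governs. Section 12.3 opens by sending patients to Table 3, Sections 13.3 and 13.4 say SpO2 is recorded according to it, and EoT is a column separate from the blinded-treatment block that carries the footnote. On that reading every discharged patient has an SpO2 value at Day 14, and the gap shrinks to Day 6 for those discharged before Day 6. This stands in part: it shows that Day 14 is ambiguous. It does not remove the problem, because a site following the explicit list would skip the reading.

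A reader might infer that recovery can never be established for anyone discharged before meeting the criteria. The Day 14 mark in Table 3 does not support so absolute a claim.

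A reader might also infer a bias against the drug. That needs the drug to speed discharge, the patients leaving early to be below 98%, and unscored patients to be counted as not recovered. The first two are unknown, and the third is not stated. Censoring or carrying the last status forward would act differently, and analysis detail is deferred to a SAP to be finalized before analysis.

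The consequence is also limited. Part 1 has no formal tests, and the neighbouring clinical improvement endpoint already credits live discharge without oxygen.

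**Conclusion.** The omission is real and appears in both places where the list is given. It is a clear gap at Day 6 for patients discharged before Day 6, and a conflict with Table 3 at Day 14 for all patients discharged early outside Bulgaria. Two secondary endpoints are exposed to missing data that depend on a post-randomization outcome.

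The size cannot be derived: the documents give neither a discharge rate nor the share of patients going home below 98%. With the planned 100 patients per group, each assumed 10% so affected would be 0.10 × 100 = 10 patients per group, but that only restates a percentage and is not an estimate. The direction of any bias is likewise open until a missing-data rule is given. The Day 28 observation rests on apparently empty cells in an extracted table and matters only if recovery is meant to be assessed up to EoS. This is a minor point that is cheap to repair.

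**What to change.** - Add SpO2 without supplemental oxygen to the Day 6 and Day 14 list in Section 12.3 and in the synopsis, and make the list, the footnote and the SpO2 row of Tables 1 and 3 agree.
- If recovery is to be assessed up to EoS, also mark temperature, respiratory rate and SpO2 at Day 28.
- State in the SAP up to which day recovery is assessed and how it is derived when a component is missing after discharge.

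The cost is one oximeter reading at each visit, already held on site with physical examination, ECG and laboratory tests, plus an eCRF line. The repair is fuller for the proportion than for the time endpoint. Recovery after discharge would still be dated only to the interval between visits: up to 14 − 6 = 8 days between the Day 6 and Day 14 visits, and 28 − 14 = 14 days between Day 14 and Day 28 if that visit is added. The SAP should say how such interval-dated recoveries enter the time-to-event analysis.

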The first dose of IMP (2 tablets) should always be given on Day 0 (allowed range for first dose: 12:00 noon on Day 0 to 02:00 a.m.). All further IMP doses are 1 tablet each in the morning and evening. For details of IMP administration see section [Test product](#). Information about the status and patient care are continuously obtained and documented once or twice daily (see [Table 1](#)). Further examinations and tests, laboratory parameters, biomarkers, disease markers, and virologic parameters are to be assessed as outlined in [Table 1](#).

After the last IMP dose in the evening of Day 13, the end-of-treatment (EoT) assessments will be done on Day 14 (see [Table 1](#)). Blood sampling for IMU-838 trough values must be performed in the morning around the time the morning dose was usually taken by the respective patient. Patients may then continue to receive SoC without any further restrictions on concomitant medications as during the 14-day BT period (see [Standard-of-care treatment](#) and [IMP-related exclusion criteria](#)).

For centers in Bulgaria: Patients must be hospitalized during the entire treatment period i.e., from Day 0 to Day 14.

For centers in countries other than Bulgaria: In case of hospital discharge before Day 14, the following assessments should be done between hospital discharge and until Day 14 (patients should return for clinic visits at Day 6, if discharged before Day 6, and Day 14):

- On the day of hospital discharge:
 - All trial-related assessments and procedures are completed as per [Table 1](#) and finalized (evening assessments should be done, even when the patient is discharged during the day)
 - The date and time of hospital discharge need to be documented
- Day 6 and Day 14:
 - The full lab assessments to be performed on Days 6 or 14, respectively (as indicated in [Table 1](#))
 - Physical examination and ECG
 - Documentation of concomitant medications/procedures, AEs, temperature, vital signs, respiratory rate, type of oxygen supplementation, survival status, hospitalization status, assessment of WHO ordinal scale¹ (only once daily assessment required)
 - Return of IMP by patients and drug accountability (Day 14 only)

If the patient is discharged from the hospital before Day 14, the patient will receive the IMP and will take the remaining doses of IMP at home.

Day 28 Visit (EoS)

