13.4 Assessment of respiratory rate and oxygen saturation

To assess the respiration of the patient, peripheral capillary oxyhemoglobin saturation (SpO₂) will be repeatedly reported (Table 3). Respiration rate will be assessed according to hospital staff's current clinical practice.

14 Pharmacokinetics, disease markers, and biomarkers

All laboratory samples for IMU-838 plasma trough levels, disease markers and biomarkers must be handled and labeled according to the respective laboratory manual i.e., virologic samples according to the manual from the central virology laboratory, all other samples according to the central safety laboratory manual.

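### SpO2 is missing from the post-discharge Day 6 and Day 14 assessment list although clinical recovery cannot be scored without it; at Day 14 the list also conflicts with Table 3

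*Combined protocol and SAP*

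**What the plan says.** Section 7 and the synopsis define the proportion of patients "with clinical recovery defined as" three conditions met together: a temperature limit, a respiratory rate of at most 24 per minute without oxygen, and an oxygen saturation of at least 98% without oxygen. A second secondary endpoint, "Time to clinical recovery", rests on the same definition. No time point is given for the proportion.

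Outside Bulgaria, patients may leave hospital before Day 14 and return on Day 6 (if already discharged by then) and on Day 14. For these visits Section 12.3 asks for full laboratory assessments, physical examination, ECG, return of study drug (Day 14 only), and "Documentation of concomitant medications/procedures, AEs, temperature, vital signs, respiratory rate, type of oxygen supplementation, survival status, hospitalization status", plus the WHO scale. The synopsis carries the same list: "Documentation of concomitant medications/procedures, AEs, temperature, vital signs, respiratory rate, type of oxygen supplementation" and so on.

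Table 3 has a separate row for SpO2: twice daily during blinded treatment, with a mark in the end-of-treatment (Day 14) column. Its footnote l reads "For assessments, if patients will be discharged from the hospital before Day 14, see" and then names the section on the blinded treatment period and Day 14.

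**The concern.** One of the three components of the endpoint is not on the list that sites are given for discharged patients. A site that follows the list has temperature, respiratory rate and type of oxygen support, and still cannot say whether the patient has recovered.

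The loss is not random. In hospital, SpO2 is read twice a day, so a qualifying reading will be caught. After discharge, observation of the endpoint stops or becomes uncertain until after Day 14. Discharge happens after randomisation and may itself respond to treatment; duration of hospitalization is one of the endpoints in Section 16.4.2 by which activity is judged. When the chance of observing an outcome depends on such a variable, the arms can differ in recorded recovery without differing in true recovery.

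**Working it through.** The plan states no figure on this point, so the check is mainly a comparison of texts.

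**1. Does another item on the list supply SpO2?**

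| Item on the list | Where defined | Gives SpO2? |
|---|---|---|
| Vital signs | Section 15.3: height, weight, temperature, "pulse rates, systolic and diastolic blood pressures" | No |
| Respiratory rate | Section 13.4, separate from SpO2, which "will be repeatedly reported" under Table 3 | No |
| Type of oxygen supplementation | Table 3, own row | No, a support category |
| Physical examination, ECG | Section 15.3 | No |
| WHO scale | Table 4 | No saturation value in any category |
| Laboratory assessments | Appendix 1 | No |

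**2. Which text governs?**
- *Day 6.* The twice-daily entry in Table 3 spans this day, but it cannot be meant literally for someone at home. The list is the only text written for that visit, and it omits SpO2.
- *Day 14.* Section 12.3 also says that end-of-treatment assessments follow Table 3, which marks SpO2. Footnote l points back to the section that holds both that sentence and the list, so it does not settle the matter. There is no precedence rule; the summary of changes records that one favouring the schedule was removed.

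**3. Does another reading close the gap?** On the day of discharge all Table 3 assessments are completed, so there is a reading then. A category 4 patient may enter with SpO2 just above 92% on oxygen, so values below 98% are expected in this population. As far as the extracted table can be read, Day 28 has no mark for SpO2, temperature or respiratory rate, so that visit does not clearly help.

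**4. Can the direction of bias be fixed?** The documents give no lengths of stay, no discharge saturations and no missing-data rule for clinical recovery. The following is therefore an illustration on assumed inputs, not an estimate. It takes the case where the list is followed at Day 14.
- R = true recovery by Day 14, equal in both arms, 60% to 80%.
- u = share sent home below 98% and not yet recovered: 10% on placebo; 15%, 20% or 30% on IMU-838.
- r = share of those who truly recover by Day 14, 50% to 90%.

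*Unscored patients counted as not recovered.* Observed recovery is R − u·r, so the difference is −(u_drug − u_placebo)·r.
- Smallest: −(0.15 − 0.10) × 0.50 = −2.5 points.
- Largest: −(0.30 − 0.10) × 0.90 = −18 points.
- With u reversed (10% on drug, 20% on placebo): +0.10 × 0.50 = +5 to +0.10 × 0.90 = +9 points.
- With u equal in both arms: 0.

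*Unscored patients excluded.* Observed recovery is (R − u·r)/(1 − u). With u of 30% on drug and 10% on placebo:
- R = 0.60, r = 0.90: 0.33/0.70 − 0.51/0.90 = 47.1% − 56.7% = −9.5 points after rounding.
- R = 0.80, r = 0.50: 0.65/0.70 − 0.75/0.90 = 92.9% − 83.3% = +9.5 points after rounding.

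The sign turns on which arm sends more patients home below 98% and on how unscored patients are handled. The documents fix neither. If SpO2 is read at Day 14, the u·r patients are scored and the artificial difference at Day 14 is 0.

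**The case against.** The strongest reply is that at Day 14 the assessment is not missing at all. Section 12.3 opens by sending patients to Table 3, repeats this for end-of-treatment, and Table 3 marks SpO2 there. A careful site would take the reading. That stands to this extent: Day 14 is a conflict to reconcile, and only Day 6, which concerns patients discharged before that day, is an outright omission. It does not dispose of the point, because a site working from the list would be equally compliant and sites may differ. Section 12.4 allows unscheduled visits whose Table 3 column includes SpO2, but these are optional.

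A reader might also infer that a drug which shortens stay will look worse on clinical recovery. The documents do not support that. It would need more IMU-838 than placebo patients to leave below 98%, and unscored patients to be treated as not recovered (or an equivalent informative censoring). Earlier discharge does not by itself mean discharge at lower saturation: if patients go home earlier because they improve earlier, the first condition may fail. The second is not written anywhere.

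Finally, the consequence is modest. Clinical recovery is one of many secondary endpoints, all of Part 1 is descriptive (Section 16.3.1), it is absent from the activity endpoints in Section 16.4.2, Bulgarian patients stay in hospital through Day 14, and endpoints are reconsidered before Part 2. All of that is correct and limits the weight of the point.

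**Conclusion.** The point holds in a limited form. Two stated secondary endpoints need SpO2, and the list for discharged patients leaves it out in both places where it appears. At Day 6 this is a plain omission; at Day 14 it contradicts Table 3 with no rule to decide between them. A patient sent home below 98% and followed by the list cannot be scored as recovered at those visits, so observation of recovery depends on discharge timing.

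This can bias the arm comparison. Neither direction nor size can be determined from the documents, and the illustrative differences above rest wholly on assumed shares; they show only that the sign is open. The conclusion about the texts needs no assumption beyond Table 3 having been extracted correctly in the Day 14 column. No primary, key secondary or Part 2 decision endpoint is affected. The change is still worth making, because a reading not taken cannot be recovered later.

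**What to change.** Add SpO2 without oxygen to the Day 6 and Day 14 post-discharge list in Section 12.3 and in the synopsis, so that it agrees with the Day 14 entry in Table 3. Use these readings, with the temperature and respiratory rate already on the list, to score clinical recovery after discharge. State in the statistical analysis plan that when recovery is first seen at a post-discharge visit, its day is interval-censored between the last assessment that did not meet the definition and that visit.

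The cost is one pulse-oximeter reading and one eCRF field at visits the patient already attends for examination, ECG and bloods. What remains is that the exact day of recovery between visits is still unobserved.
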